#### 7.8.1.3. **Adverse Drug Reaction**

An adverse drug reaction (ADR) in the pre-approval clinical experience with a new medicinal product or its new usages, particularly as the therapeutic dose(s) may not be established, is any noxious and unintended response to a medicinal product related to any dose. The phrase "responses to a medicinal product" means that a causal relationship between a medicinal product and an AE is at least a reasonable possibility (ie, the relationship cannot be ruled out).

#### 7.8.1.4. Adverse Events of Special Interest

Based on the mechanism of action of olorinab and prior experience with other agents acting via a similar mechanism, potential AEs of special interest may be identified. In addition to appropriate reporting of these events as an AE or SAE, supplementary detailed information may be collected.

#### **7.8.1.5.** Severity

The severity of each AE will be assessed at the onset by a nurse/or physician. When recording the outcome of the AE the maximum severity of the AE experienced will also be recorded. The severity of each AE will be graded according to CTCAE, version 5.0:

Grade 1: Mild; asymptomatic or mild symptoms; clinical or diagnostic

observations only; intervention not indicated

Grade 2: Moderate; minimal, local or noninvasive intervention indicated;

limiting age-appropriate instrumental activities of daily living

Grade 3: Severe or medically significant but not immediately life-threatening;

hospitalization or prolongation of hospitalization indicated; disabling,

limiting self-care activities of daily living (eg, preparing meals, shopping for groceries or clothes, using the telephone, managing

money)

Grade 4: Life-threatening consequences, urgent intervention indicated

Grade 5: Death related to AE

## 7.8.1.6. Relationship

The Investigator is obligated to assess the relationship (causal relationship) between the study treatment and each occurrence of each AE/SAE. The AE relationship (causal relationship) to study treatment must be characterized as one of the following categories:

Not Related: The AE does not follow a reasonable temporal sequence from

administration of the study treatment, does not abate upon

discontinuation of the study treatment, does not follow a known or hypothesized cause-effect relationship, and (if applicable) does not reappear when the study treatment is reintroduced, furthermore, there may exist a clear alternative medical explanation (eg, underlying disease state) or association with study procedure or study conduct.

Unlikely Related: The temporal association between the AE and the study treatment is

such that the study treatment is not likely to have any reasonable

association with the AE.

Probably Related: The AE follows a reasonable temporal sequence from administration of

the study treatment and cannot be reasonably explained by the known characteristics of the subject's clinical state, environmental, or toxic factors, or other modes of therapy administered to the subject.

Related: The AE follows a reasonable temporal sequence from administration of

the study treatment, abates upon discontinuation of the study treatment, follows a known or hypothesized cause-effect relationship, and (if appropriate) reappears when the study treatment is reintroduced.

The Investigator will use clinical judgment to determine the relationship (causal relationship). Alternative causes, such as underlying disease(s), concomitant therapy, and other risk factors, as well as the temporal relationship of the event to the study treatment administration should be considered and investigated. The Investigator should consult the Investigator's Brochure and the Product Information of marketed products within the drug class, when applicable. For each AE/SAE, the Investigator must document in the source documents that he/she has reviewed the AE/SAE and has provided an assessment of causality. There may be situations in which an SAE has occurred and the Investigator has minimal information to include in the initial report to the Sponsor; however, it is very important that the Investigator always makes an initial assessment of causality for every event before the initial transmission of the SAE to the Sponsor. The Investigator may change his/her opinion of causality based on subsequent receipt of information and send an SAE follow-up report with the updated causality assessment. The causality assessment is one of the criteria used when determining regulatory reporting requirements.

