#### 7.8.2.6. Serious, Unexpected Adverse Drug Reactions

All ADRs that are both serious and unexpected are subject to expedited reporting to regulatory agencies. An unexpected ADR is one for which the nature or severity is not consistent with information in the relevant source documents.

The following documents or circumstances will be used to determine whether an AE/ADR is expected:

- 1. For a medicinal product not yet approved for marketing in a country, the reference safety information section of a company's Investigator's Brochure will serve as the source document in that country
- 2. Reports that add significant information on specificity or severity of a known, already documented serious ADR constitute unexpected events. For example, an event more specific or more severe than described in the Investigator's Brochure would be considered "unexpected"

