#### 19.1.3. RELATIONSHIP TO STUDY TREATMENT

Relationship is classed as "not related", "unlikely related", "probably related", or "related" (increasing severity of relationship) by the Investigator. A "related" TEAE for the purpose of TEAE summaries is defined as a TEAE with a relationship to study treatment as "related" or "probably related" to study treatment. TEAEs with a missing relationship to study treatment will be regarded as "related" to study treatment. "Unlikely related" will be counted as non-related TEAE. If a subject reports the same AE more than once within the same SOC/PT, the AE with the strictest causality will be used in the corresponding relationship summaries. All TEAEs will be summarized by SOC, PT, and relationship to study treatment.

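### The four-level causality scale in Protocol 7.8.1.6 does not match the adverse drug reaction definition in 7.8.1.3: some adverse events with plausible timing that IBS could also explain fit no category

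*Protocol*

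**What the plan says.** Protocol 7.8.1.6 makes the grading compulsory: "The AE relationship (causal relationship) to study treatment must be characterized as one of the following categories". The four categories are worded as follows.

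- Not Related opens with timing ("Not Related: The AE does not follow a reasonable temporal sequence from" dosing) and adds no resolution on stopping, no causal link and no recurrence.
- Unlikely Related is defined by the time relation alone, one "such that the study treatment is not likely to have any reasonable" association with the event.
- Probably Related needs timing that fits "the study treatment and cannot be reasonably explained by the known" features of the subject's clinical state, by environmental or toxic factors, or by other treatments.
- Related needs fitting timing, resolution on stopping, a recognised or postulated causal link and, if appropriate, recurrence on reintroduction. It does not require that other explanations be excluded.

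The same section leaves the choice to clinical judgment, with timing and alternative causes both to be considered. It names no default category.

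Protocol 7.8.1.3 sets a lower bar for an adverse drug reaction (ADR): a causal link that is "at least a reasonable possibility (ie, the relationship cannot be ruled out". Protocol 7.8.2.6 then says: "All ADRs that are both serious and unexpected are subject to expedited reporting to regulatory agencies".

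Main Study SAP 19.1.3 and LTE SAP 18.1.3 share one rule. Related and Probably Related count as related, and so does a missing grade. An Unlikely Related event "will be counted as non-related TEAE".

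**The concern.** The ADR definition asks whether a link can be excluded. The scale has no level for that answer. The lowest level that counts as related is Probably Related, which asks that other explanations be set aside.

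The gap is relevant in this population. Protocol 1.2 lists diarrhea among the most frequent TEAEs seen with olorinab. Enrolment is planned at about equal numbers of IBS-C and IBS-D, so roughly 240 / 2 = 120 subjects have a disease of which diarrhea is a defining symptom.

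The one open route, Related, is often hard to use. If treatment continues, resolution on stopping cannot be observed. For serious events, 7.8.1.6 wants a causality call before the first transmission even when information is minimal. Protocol 3.2 also expects no effect of olorinab on diarrhea or constipation, which may discourage an investigator from naming a causal link.

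Safety and tolerability by dose is a primary objective. Main Study SAP 19.1.1 and 19.1.9 plan summaries of related TEAEs, related serious TEAEs and related TEAEs leading to discontinuation or interruption. Causality is also one input to regulatory reporting (Protocol 7.8.1.6).

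**Working it through.** The plan gives no figure on this point, so there is nothing to reproduce. The check applies the four definitions in Protocol 7.8.1.6 literally to one kind of event: timing is plausible, and the subject's IBS could also reasonably explain it.

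| Category | Deciding condition | Result for this event |
|---|---|---|
| Not Related | timing does not fit | fails |
| Unlikely Related | timing makes causation unlikely | fails |
| Probably Related | no other reasonable explanation | fails |
| Related | resolves on stopping, causal link, recurrence if tested | met only if all hold |

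**Counting the profiles.** The remaining features are:

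- outcome on stopping: resolves, persists, or treatment not stopped (3 levels);
- recognised or postulated causal link: yes or no (2 levels);
- rechallenge: recurs, does not recur, or not applicable (3 levels; only not applicable if treatment was never stopped).

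Treatment stopped: 2 × 2 × 3 = 12 profiles. Not stopped: 1 × 2 × 1 = 2. Total: 14.

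Profiles that meet Related (resolves, link present, recurs or not applicable): 1 × 1 × 2 = 2.

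Profiles that meet no category: 14 − 2 = 12. Both profiles in which treatment continues are among these 12. These are logical combinations; they are not equally likely and say nothing about how many events to expect.

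**Against the ADR definition.** Plausible timing plus a competing explanation does not exclude the drug. An event in any of the 12 profiles can therefore meet 7.8.1.3 and still have no category in 7.8.1.6.

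**Against the SAPs.** The same event is tabulated according to where the investigator happens to put it:

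- Related or Probably Related: counted as related;
- Unlikely Related or Not Related: counted as non-related;
- left blank: counted as related.

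A blank field thus counts towards the drug, while a considered judgment that it could be drug or disease may not.

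**Size.** In one arm, let A be the number of subjects whose only candidate related event fits no category, and u the share of them graded Unlikely Related or Not Related. The related count is then lower by u × A. With u anywhere from 0 to 1, the loss runs from 0 to A. The documents give neither A nor u.

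**The case against.** A reader might infer more: that the scale has no place at all for these events, that they fall to Unlikely Related by rule, that drug-related GI reactions therefore vanish from the safety evaluation, and that serious ones escape expedited reporting. The documents do not support this.

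- Unlikely Related is worded on timing, so a plausible-timing event fails it as clearly as it fails Probably Related. Nothing makes it the default. An investigator could choose either.
- Related stays open to an event that IBS could explain, as two of the 14 profiles show.
- The primary safety endpoint is adverse events regardless of causality (Protocol 8.3.1.1). All TEAEs are tabulated by system organ class and preferred term (Main Study SAP 19.1 and 19.1.1), so an imbalance in diarrhea between doses would remain visible.
- Every SAE goes to the sponsor's contact within 24 hours whatever its causality (Protocol 7.8.2.5). Expedited reporting in 7.8.2.6 is tied to the ADR definition and not to the SAP's related/non-related split. No section says that an Unlikely Related grade removes an event from that assessment.
- An IBS explanation is not always available even in IBS-D. A TEAE must be new or worse after dosing, and worsening beyond a subject's known pattern may still qualify as Probably Related. Nausea, also on the Protocol 1.2 list, is not among the IBS symptoms named in the Protocol introduction.

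All of this stands, and it limits the consequences. It does not supply a category for the remaining events or reconcile 7.8.1.6 with 7.8.1.3. There is also a point on timing: LTE SAP 4.3 says the Main Study analysis was complete and the LTE was being ended early, so a new eCRF level could do little for data already collected.

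**Conclusion.** The scale is wrong as written. A plausible-timing event that IBS could also explain, and that does not meet Related, has no category, even though the protocol's own ADR definition can include it. Assignment is left to judgment and may differ between investigators. Any such event graded Unlikely Related is counted as non-related in both SAPs.

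The effect is limited to the related-TEAE summaries and to the causality input to expedited reporting. All-TEAE tables and 24-hour SAE reporting to the sponsor are unaffected. The number of events involved cannot be computed from the documents.

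The conclusion rests on a literal reading of the four definitions, in particular of Unlikely Related as a statement about timing only.

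**What to change.** Reconcile Protocol 7.8.1.3 and 7.8.1.6:

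1. Add a Possibly Related level to 7.8.1.6 and the AE eCRF, for reasonable timing when other explanations are also possible.
2. State that Possibly, Probably and Related all meet the ADR definition for 7.8.2.6.
3. Count Possibly Related as related in Main Study SAP 19.1.3 and LTE SAP 18.1.3.
4. For events already graded on the four-level scale, add one sensitivity summary in which every TEAE not graded Not Related is counted as related.

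Item 4 needs no new data. Both SAPs already plan TEAEs by relationship category and take the strongest causality per subject and term. If that table shows the four grades separately, adding Unlikely, Probably and Related (with missing grades already counted as Related) gives the subject count for each preferred term. It cannot recover ambiguous events graded Not Related. If it is produced after the SAP was approved, it should be identified in the study report as unplanned, as Main Study SAP 5.2 and LTE SAP 5.1 require.

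The cost is one eCRF option, some wording and one table. The downside is that related-AE percentages rise slightly and more SAEs are assessed for expedited reporting.

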#### 7.8.2. Eliciting and Recording Adverse Events

#### 7.8.2.1. Eliciting Adverse Events

Subjects will be instructed that they may report AEs at any time. An open-ended or nondirected method of questioning should be used at each study visit to elicit the reporting of AEs.

#### 7.8.2.2. Recording Adverse Events

The AE reporting period for safety surveillance begins when the subject is initially included in the study (date of first signature of informed consent) and continues up to 30 days after the last study treatment administration. If an AE is not resolved or stabilized by this time, the Sponsor in consultation with the Investigator will decide whether to continue to monitor the AE or closeout the event in the database if no further follow-up is necessary.

Any SAE suspected to be related to the study treatment must be reported whenever it occurs, irrespective of the time elapsed since the last administration.

Investigator and study personnel will record all AEs and SAEs whether received through an unsolicited report by a subject, elicited during subject questioning, discovered during physical examination, laboratory testing, and/or other means by recording them on the eCRF as appropriate. To avoid vague, ambiguous, or colloquial expressions, the AE should be recorded on the source documents and/or eCRFs using standard medical terminology that is as specific as possible, rather than the subject's own words. Whenever the Investigator is confident in making

a unifying diagnosis, all related signs, symptoms, and abnormal test results should be grouped together as a single AE in the source document and/or eCRF (eg, cough and rhinitis should be reported as an "upper respiratory tract infection").

The Investigator should assess when it may be appropriate for intermittent events of the same type to be grouped together as a single AE in the source document and/or eCRF (eg, "intermittent headache").

The following information should be recorded on the AE eCRF:

- Description including onset and resolution dates
- Whether it met SAE criteria
- Severity
- Relationship to study treatment or other causality
- Outcome

For SAEs, events occurring secondary to the primary event should be described on the eCRF in the narrative description field.

The following should be considered when recording SAEs:

- Death is an outcome of an event. The event that resulted in the death should be recorded and reported on the eCRF
- For hospitalizations, surgical, or diagnostic procedures, the illness leading to the surgical or diagnostic procedure should be recorded as the SAE, not the procedure itself. The procedure should be captured in the narrative as part of the action taken in response to the illness.

#### 7.8.2.3. Diagnosis Versus Signs or Symptoms

In general, the use of a unifying diagnosis is preferred to the listing out of individual symptoms. Grouping of symptoms into a diagnosis should generally be limited to occasions when each component sign and/or symptom is a medically confirmed component of a diagnosis as evidenced by standard medical textbooks. If an aspect of a sign or symptom does not fit into a classic pattern of the diagnosis in the clinical judgement of the investigator, the individual symptom should generally be reported as a separate AE.

#### 7.8.2.4. Reporting Serious Adverse Events

All SAEs are subject to reporting requirements.

#### 7.8.2.5. Serious Adverse Events

All SAEs, whether or not considered related to study treatment, must be reported to the designated Sponsor Contact within 24 hours of becoming aware of the event. Enter the SAE information into the electronic data capture (EDC) system, and send other available pertinent information (eg, hospital records, laboratory results) to the designated Sponsor Contact:

IQVIA Pharmacovigilance		
Phone:		
Fax:		
Email:		

If additional follow-up information is required or becomes available for a previously reported SAE, entry of the new information into EDC should be completed within 24 hours of awareness.

Elective hospitalization and/or surgery for clearly preexisting conditions (eg, a surgery that has been scheduled prior to the subject's entry into the study) will not be reported as an SAE. All other hospitalizations, including elective hospitalizations for any condition that was not preexisting, will be reported as an SAE.

Any SAE that is ongoing when the subject completes the study or discontinues the study will be followed by the Investigator until the event resolved, stabilized or returned to baseline (Main Study Visit 3 or LTE Visit 2, as applicable) status.

#### 7.8.2.6. Serious, Unexpected Adverse Drug Reactions

All ADRs that are both serious and unexpected are subject to expedited reporting to regulatory agencies. An unexpected ADR is one for which the nature or severity is not consistent with information in the relevant source documents.

The following documents or circumstances will be used to determine whether an AE/ADR is expected:

- 1. For a medicinal product not yet approved for marketing in a country, the reference safety information section of a company's Investigator's Brochure will serve as the source document in that country
- 2. Reports that add significant information on specificity or severity of a known, already documented serious ADR constitute unexpected events. For example, an event more specific or more severe than described in the Investigator's Brochure would be considered "unexpected"

## 7.9. Pregnancy

If at any point a urine or serum hCG pregnancy test is positive, the subject will be withdrawn from the study treatment.

Details of all pregnancies that occur in female subjects and female partners of male subjects after the start of study treatment and until 30 days after the last dose will be collected.

Pregnancy (during maternal or paternal exposure to study treatment) does not meet the definition of an AE; however, to fulfill regulatory requirements, any pregnancy should be reported via the Pregnancy Report Form to the designated Sponsor Contact within 24 hours of awareness to collect data on the outcome of the birth for both the mother and the fetus.

Abnormal pregnancy outcomes (eg, spontaneous abortion, fetal death, stillbirth, congenital anomalies, ectopic pregnancy) are considered SAEs and should be reported as such even if outside the SAE reporting period.

#### 7.10. Pharmacokinetics

Samples will be used to evaluate the PK of olorinab and its predominant metabolites

Samples collected for analyses of these olorinab plasma concentrations may also be used for profiling of drug binding proteins, bioanalytical method validation, stability assessments, metabolite assessments, to assess other actions of olorinab (and/or its metabolites) with plasma constituents, or for context pertaining to safety events arising during or after the study.

During the Main Study, calculated plasma PK parameters of olorinab and its metabolites will include but not necessarily be limited to the following:

- Cmax observed maximum concentration
- tmax time of observed maximum (peak) concentration after drug administration
- Ctrough observed trough (pre-dose) concentration

During the LTE, only Ctrough will be calculated.

Subject confidentiality will be maintained.

Drug concentration information that would unblind the study will not be reported to investigative sites or blinded personnel until the study has been unblinded. Detailed instructions regarding sample collection, processing, and shipping will be provided in a separate Laboratory Manual.

## 7.11. Pharmacodynamics

Pharmacodynamic parameters are not evaluated in this study.

#### 7.12. Genetics

A blood sample for deoxyribonucleic acid (DNA) isolation will be collected from subjects who have consented to participate in the genetic analysis component of the study. Participation is optional. Subjects who do not wish to participate in the genetic research may still participate in the study.

In the event of DNA extraction failure, a replacement genetic blood sample may be requested from the subject. Signed informed consent will be required to obtain a replacement sample unless it was included in the original consent.

Details on processes for collection and shipment and destruction of these samples can be found in the Laboratory Manual.

Samples may be stored for a maximum of 20 years (or according to local regulations) following the last subject's last visit for the study at a facility selected by the Sponsor to enable further analysis of genetic samples.

#### 7.13. Biomarkers

Colonic biopsy and blood biomarker samples will be collected from subjects who have consented to participate in the colonic biopsy and blood biomarker component of the study. Collection of blood samples for exploratory biomarker assessments will be collected at all sites. Blood samples may be tested for cytokines and chemokines. Collection of colonic biopsy samples for exploratory biomarker assessments will be collected at select sites only. Colonic biopsy tissue may be tested for components of the endocannabinoid system. Additional biomarkers in blood or colonic biopsies as deemed relevant to assess efficacy and mechanism of action of olorinab may be evaluated. Collection of colonic biopsy and biomarker samples will be conducted

Details for collection, processing, and storage will be provided in the Laboratory Manual. Residual samples will be stored and may be used for additional analyses to further explore efficacy and mechanism of action of olorinab if the subject has granted optional consent for such testing. These additional analyses will only be conducted where allowed by the regulatory authorities and local ethics committees.

Samples may be stored for a maximum of 20 years (or according to local regulations) following the last subject's last visit for the study at a facility selected by the Sponsor to enable further analysis of biomarker responses to olorinab.

